***Recommended guidelines for use of oral diabetic agents:**

Initiation of treatment for hyperglycemia should occur under the guidance of a pediatric endocrinologist at the local institution. Metformin or other oral anti-hyperglycemia agent may be used per local endocrinologist's recommendations. Insulin therapy should be directed by specialists in pediatric diabetes, with the goal of normal fasting blood sugars < 126 mg/dL and HgbA1C $< 8\%$.

7.0 SUPPORTIVE CARE AND OTHER CONCOMITANT THERAPY

7.1 **Concurrent Anticancer Therapy**

Concurrent cancer therapy, including chemotherapy, radiation therapy, immunotherapy, or biologic therapy may NOT be administered to patients receiving study drug. If these treatments are administered the patient will be removed from protocol therapy.

7.2 **Investigational Agents**

No other investigational agents may be given while the patient is on study.

7.3 **Supportive Care**

Appropriate antibiotics, blood products, antiemetics (except aprepitant), fluids, electrolytes and general supportive care are to be used as necessary. See [Appendix VIII](#) for information on management of irinotecan-induced diarrhea. See [Appendix X](#), [Appendix XIII](#), and [Appendix XIV](#) for drugs that should not be used concomitantly due to potential interactions with ABI-009, irinotecan, or temozolomide.

Please refer to COG Supportive Care Guidelines found under the Protocol Reference Materials tab under Standard Sections for Protocols at <https://childrensoncologygroup.org/index.php/cog-supportive-care-guidelines>.

7.4 **Growth Factors**

Growth factors that support platelet or white cell number or function can only be administered in accordance with [Section 6.2](#) or for culture proven bacteremia or invasive fungal infection. The Study Chair should be notified before growth factors are initiated.

7.5 **Concomitant Medications (Study Specific)**

- a. HMG-CoA reductase inhibitors may be used to treat elevated fasting triglycerides and cholesterol. See [Section 6.4](#) and [Section 6.5](#).

While on study, the following BCRP inhibitors (cyclosporine, eltrombopag, gefitinib) should be avoided if possible, and concomitant use of UGT1A1 inhibitors, such as diclofenac, ketoconazole, probenecid, silibinin, nilotinib and atazanavir, should be avoided because of potential for increased irinotecan toxicity.

Because rapamycin is a substrate for both CYP3A4 and P-gp, concomitant administration with inhibitors or inducers of CYP3A4 and P-gp may alter the pharmacokinetics of ABI-009. Inhibitors of CYP3A4 may decrease the metabolism of rapamycin and increase rapamycin concentrations, while inducers of CYP3A4 may increase the metabolism of rapamycin and decrease rapamycin concentrations. Drugs that may increase rapamycin blood concentrations include antifungal agents (e.g., voriconazole, itraconazole, posaconazole), macrolide antibiotics (e.g., clarithromycin, telithromycin), and other drugs (e.g., HIV-protease inhibitors). Drugs that may decrease rapamycin concentrations include anticonvulsants (e.g., carbamazepine, phenobarbital, phenytoin), and antibiotics (e.g., rifabutin, rifampin). See [Appendix XIV](#) for more information on CYP3A4 inducers and inhibitors.

8.0 **EVALUATIONS/MATERIAL AND DATA TO BE ACCESSIONED**

8.1 **Required Clinical, Laboratory and Disease Evaluation**

All clinical and laboratory studies to determine eligibility must be performed within 7 days prior to enrollment unless otherwise indicated. Laboratory values used to assess eligibility (see [Section 4.0](#)) must be no older than seven (7) days at the start of therapy. Laboratory tests need **not** be repeated if therapy starts **within** seven (7) days of obtaining labs to assess eligibility. If a post-enrollment lab value is outside the limits of eligibility, or laboratory values are older than 7 days, then the following laboratory evaluations must be re-checked within 48 hours prior to initiating therapy: CBC with differential, bilirubin, ALT (SGPT) and serum creatinine. If the recheck is outside the limits of eligibility, the patient may not receive protocol therapy and will be considered off protocol therapy. Imaging studies must be obtained within 14 days prior to start of protocol therapy (repeat the tumor imaging if necessary).

STUDIES TO BE OBTAINED	Pre-Study	Cycles 1 & 2	Prior to Subsequent Cycles [^]
History	X	Weekly	X
Physical Exam with vital signs	X	Weekly	X
Height, weight, BSA	X	Prior to Cycle 2	X
Performance Status	X	Prior to Cycle 2	X
CBC, differential, platelets	X	Twice Weekly (every 3 to 4 days) ³	Weekly ⁴
Pharmacokinetics ¹	X	X	
Urinalysis	X		
Electrolytes including Ca ⁺⁺ , PO ₄ ³⁻ , Mg ⁺⁺ , glucose ¹¹	X	Weekly	X
Creatinine, ALT, bilirubin	X	Weekly	X
Albumin	X	Prior to Cycle 2	X
INR	X		
Total Cholesterol, Triglycerides ¹⁰	X	Weekly	X
Amylase, Lipase	X	Prior to Cycle 2	X
Pregnancy Test ²	X		
Tumor Disease Evaluation	X	End of Cycles 1 ¹² & 2	Every other cycle x 2 then q 3 cycles ⁵
Bone Marrow Evaluation ⁷	X		
Medication Diary ⁶		Cycle 2	X
Oxygen Saturation	X	Weekly	X ⁸
Tumor Tissue Studies ⁹	X		

[^] Studies may be obtained within 72 hours prior to the start of the subsequent cycle.

¹ See [Section 8.3](#) for timing of PK studies.

² Women of childbearing potential require a negative pregnancy test prior to starting treatment; sexually active patients must use an acceptable method of birth control. Abstinence is an acceptable method of birth control.

³ If patients have Grade 4 neutropenia then CBCs should be checked at least every 2-3 days until recovery to Grade 3 or until meeting the criteria for dose limiting toxicity.

⁴ If patients develop Grade 4 neutropenia or Grade 4 thrombocytopenia then CBCs should be checked every 3 to 4 days until recovery to Grade 3

⁵ Tumor Disease Evaluation should be obtained on the next consecutive cycle after initial documentation of either a PR or CR. Subsequent scans may restart 2 cycles after the confirmatory scan. Please note that for solid tumor patients, if the institutional investigator determines that the

- patient has progressed based on clinical or laboratory evidence, he/she may opt not to confirm this finding radiographically.
- ⁶ Medication diary (see [Appendix IX](#)) should be reviewed after completion of each treatment cycle and uploaded into RAVE.
- ⁷ As appropriate for disease, to confirm bone marrow involvement at enrollment, or as clinically indicated.
- ⁸ Required prior to each cycle; weekly for subsequent cycles only if clinically indicated.
- ⁹ See [Section 8.4](#) and [Appendix XII](#) for details of Tumor Tissue studies.
- ¹⁰ If Grade 3 or 4 hypercholesterolemia or Grade 3 or 4 hypertriglyceridemia is detected when routine (non-fasting) laboratory studies are performed, the tests should be repeated within 3 days in the fasting state to permit accurate grading.
- ¹¹ If the initial blood glucose is a random sample that is outside of the normal limits, then follow-up fasting blood glucose can be obtained and must be within the upper normal limits for age. If blood glucose is $\geq 250 - 500$ mg/dL or $> 13.9 - 27.8$ mmol/L when routine (non-fasting) laboratory studies are performed, the test should be repeated within 3 days in the fasting state to permit accurate grading.
- ¹² Patients experiencing progressive disease (defined in Section 12.6.4) in Cycle 1 can continue to Cycle 2 as long as 1) they have not experienced a DLT in Cycle 1, 2) they have not met any off study criteria listed in section 10.2, and 3) they meet all guidelines established in section 5.2. Patients must have at least stable disease to continue to Cycles 3 and later.

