2.3 Adult Studies

2.3.1 Phase 1 Studies

The first in-human trial of ABI-009 administered at 5 dose levels (45, 56.25, 100, 125, and 150 mg/m²) on a weekly schedule for 3 weeks followed by 1 week of rest in patients with advanced solid tumors. The maximum tolerated dose (MTD) was 100 mg/m² with the most common toxicities including thrombocytopenia (58%), hypokalemia (23%), mucositis (38%), fatigue (27%), rash (23%), diarrhea (23%),

nausea (19%), anemia (19%), hypophosphatemia (19%), neutropenia (15%), and hypertriglyceridemia (15%). The study initially dose escalated from 100 mg/m² to 150 mg/m² which resulted in 4 dose-limiting toxicities (DLTs), two at 150 mg/m² and two at 125 mg/m²; these were grade 3 AST elevation and grade 4 thrombocytopenia and grade 3 suicidal ideation and grade 3 hypophosphatemia, respectively (CTCAE v.4). The MTD had only 1 grade 3 non-hematologic event (dyspnea) and 1 grade 3 hematologic event (anemia) after cycle 1 (CTCAE v4). Twenty-seven patients were enrolled on this trial; however, only 19 were evaluable for efficacy. There was 1 patient with adenocarcinoma of the kidney with a partial response, two patients with stable disease (mesothelioma and neuroendocrine tumor) with prolonged stabilization for 1 year and 238 days, respectively.²¹

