5.5.1 Non-hematological dose-limiting toxicity

5.5.1.1 Any Grade 3 or greater non-hematological toxicity attributable to the protocol therapy with the specific exclusion of:

- Grade 3 nausea and vomiting < 3 days duration
- Grade 3 liver enzyme elevation, including ALT/AST/GGT, that returns to Grade ≤ 1 or baseline prior to the time for the next treatment cycle.
Note: For the purposes of this study the ULN for ALT is defined as 45 U/L and the ULN for AST is defined as 50 U/L, regardless of baseline. See [Appendix XV](#) for values that represent thresholds between CTCAE grades for ALT, AST, GGT and bilirubin.
- Grade 3 fever
- Grade 3 infection
- Grade 3 hypophosphatemia, hypokalemia, hypocalcemia or hypomagnesemia responsive to supplementation.
- Grade 3 or 4 hypertriglyceridemia that returns to Grade ≤ 2 prior to the start of the next treatment cycle. The severity (grade) of hypertriglyceridemia is based upon fasting levels. If Grade 3 or 4 triglycerides are detected when routine (non-fasting) laboratory studies are performed, the test should be repeated within 3 days in the fasting state to permit accurate grading (see [Section 6.4](#)).
- Grade 3 hyperglycemia that returns to a fasting glucose value ≤ 250 mg/dL or a fasting glucose of value ≤ 13.9 mmol/L (with or without the use of insulin or oral diabetic agents) prior to the start of the next treatment cycle. Medical management of hyperglycemia should be based on fasting levels. If routine (non-fasting) laboratory studies are performed and indicate the potential for intervention, the test should be repeated within 3 days in the fasting state to permit accurate medical management and grading (see [Section 6.6](#)).
- Grade 3 or 4 hypercholesterolemia that returns to \leq Grade 2 after initiation of lipid lowering medication prior to the next treatment cycle. The severity (grade) of hypercholesterolemia is based upon fasting levels. If Grade 3 or 4 hypercholesterolemia is detected when routine (non-fasting) laboratory studies are performed, the test should be repeated within 3 days in the fasting state to permit accurate grading (see [Section 6.5](#)).

5.5.1.2 Non-hematological toxicity that causes a delay of > 21 days between treatment cycles.

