APPENDIX XV: TOXICITY-SPECIFIC GRADING

Bilirubin

Grade 1:	> ULN- ≤ 1.5 x ULN
Grade 2:	> 1.5 x ULN- 3.0 x ULN
Grade 3:	> 3.0 x ULN -10.0 x ULN
Grade 4:	> 10.0 x ULN

ALT: For the purpose of this study, the ULN for ALT is 45 U/L regardless of baseline.

Grade 1:	> 45 U/L- ≤ 135 U/L
Grade 2:	136 U/L - 225 U/L
Grade 3:	226 U/L - 900 U/L
Grade 4:	> 900 U/L

AST: For the purpose of this study, the ULN for AST is 50 U/L regardless of baseline.

Grade 1:	> 50 U/L ≤ 150 U/L
Grade 2:	151 U/L -250 U/L
Grade 3:	251 U/L -1000 U/L
Grade 4:	> 1000 U/L

GGT:

Grade 1:	> ULN- 2.5 x ULN
Grade 2:	> 2.5 x ULN - 5.0 x ULN
Grade 3:	> 5.0 x ULN -20.0 x ULN
Grade 4:	> 20.0 x ULN

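### AST and GGT elevations count towards DLT, but the required laboratory schedule contains neither test, so a DLT-level rise not mirrored in ALT or bilirubin can go unrecorded

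*Combined protocol and SAP*

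**What the plan says.** Section 5.5.1.1 defines non-hematological DLT as "Any Grade 3 or greater non-hematological toxicity attributable to the protocol therapy with the specific exclusion of" a list of exceptions. One exception is "Grade 3 liver enzyme elevation, including ALT/AST/GGT, that returns to Grade" ≤1 or to baseline before the next cycle is due. An attributable Grade 3 AST or GGT elevation that does not recover in time is therefore a DLT, and so is any attributable Grade 4 elevation.

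The same section states that "the ULN for AST is defined as 50 U/L, regardless of baseline", and Appendix XV repeats this and sets grade limits for AST. It grades GGT as multiples of the ULN.

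The required schedule in Section 8.1 has one liver chemistry row, "Creatinine, ALT, bilirubin", due pre-study, weekly in Cycles 1 and 2, and before later cycles. The panel to be rechecked before therapy starts is "CBC with differential, bilirubin, ALT (SGPT) and serum creatinine". Liver eligibility in Section 4.1.8.3 uses bilirubin, ALT and albumin. None of these places, and no footnote to the schedule, asks for AST or GGT.

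Section 11.2.1 makes evaluability for DLT depend on appropriate toxicity monitoring having been done, but names no tests.

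**The concern.** The DLT rule refers to two analytes that the schedule never requires. A patient can have every scheduled test done, be evaluable, and be counted as free of DLT with no AST or GGT value on file. If a site does order AST and finds it high, the recovery exclusion calls for a baseline and a follow-up value, and neither is required.

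AST is a plausible signal for this regimen. The adult ABI-009 trial's DLTs, as reported in Section 2.3.1, included "grade 3 AST elevation and grade 4 thrombocytopenia". The temozolomide toxicity table (Section 9.4.2) lists AST increase as common (>20%). The irinotecan table (Section 9.3.2) lists it at 4-20% and does not list ALT. The reporting exceptions in Section 13.1 name AST increase but not ALT.

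What is at stake is uniform DLT ascertainment at Dose Level -2, where Section 11.3.1 decides on a count in six patients, and the description of toxicity, which is a primary aim (Sections 1.1.2 and 1.1.3).

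**Working it through.** **1. Is AST grading fully defined?** Appendix XV states "For the purpose of this study, the ULN for AST is 50 U/L regardless of baseline". Its limits follow from multiples of the ULN:

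- AST: 3 × 50 = 150, 5 × 50 = 250, 20 × 50 = 1000 U/L, so Grade 3 is 251-1000 and Grade 4 is above 1000.
- ALT: 3 × 45 = 135, 5 × 45 = 225, 20 × 45 = 900 U/L.

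Both agree with the printed limits. The grading is complete; what is missing is a required test to supply the value.

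**2. Rule against schedule.**

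| Analyte | Named in DLT rule (5.5.1.1) | Graded in Appendix XV | Required pre-study | Required in Cycles 1-2 |
|---|---|---|---|---|
| ALT | yes | yes | yes | weekly |
| AST | yes | yes | no | no |
| GGT | yes | yes | no | no |
| Bilirubin | under the general Grade ≥3 rule | yes | yes | weekly |

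The DLT window is Cycles 1 and 2 (Section 5.5). With 21-day cycles, weekly testing gives nominally 3 × 2 = 6 on-study ALT values and no AST or GGT values.

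**3. Where a missed event would enter the decision.** Section 11.3.1 treats Dose Level -2 as tolerable with at most 1 DLT in 6 evaluable patients and closes accrual with 2 or more. Section 11.2.2 qualifies this: two DLTs of different classes in 6 may lead to consideration of expansion to 12, under stated conditions. Section 11.1.1 still budgets for that expansion at this level: (12 + 6) / (1 − 0.30) = 25.7, rounded up to the stated 26 additional patients. DLTs in the PK expansion also count towards the MTD.

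**4. Illustration of size, on assumed rates.** The documents give no rate of DLTs visible only through AST or GGT. Let b be the rate of all other DLTs and q the rate of such otherwise unseen DLTs, in patients with no other DLT. The chance of at most 1 DLT in 6 at total rate p is (1−p)^6 + 6p(1−p)^5, with p = b if the tests are never done and p = b + q if they always are. For b = 20% and no testing: 0.8^6 + 6 × 0.2 × 0.8^5 = 0.262 + 0.393 = 0.655.

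| b | tests never done | q = 2%, tests done | q = 5%, tests done | q = 10%, tests done |
|---|---|---|---|---|
| 15% | 77.6% | 72.9% | 65.5% | 53.4% |
| 20% | 65.5% | 60.6% | 53.4% | 42.0% |
| 25% | 53.4% | 48.7% | 42.0% | 31.9% |

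At q = 0 there is no difference. At q = 2% the chance of passing is overstated by about 5 percentage points. At q = 10% the overstatement is 21.5 to 24 points, but nothing in the documents supports a q that high. The calculation treats the six patients as a fixed set and ignores the mixed-class exception.

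**The case against.** The strongest reply is that hepatic toxicity is already monitored. ALT and bilirubin are required weekly throughout the DLT window, and in the closest regimen, temsirolimus with irinotecan and temozolomide in children, the hepatic DLT that Section 2.1.4 reports was ALT. This stands and limits the point: a reader might infer that the plan does not look for liver DLTs, and that is not so.

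A reader might also take the adult trial as a direct precedent. Section 2.3.1 says of the two DLTs at 150 mg/m² and the two at 125 mg/m²: "these were grade 3 AST elevation and grade 4 thrombocytopenia and grade 3 suicidal ideation and grade 3 hypophosphatemia, respectively". That places the AST event at 150 mg/m², ten times the 15 mg/m² of Dose Level -2. It was Grade 3, and the text does not say whether it recovered, so under Section 5.5.1.1 it might not have been a DLT at all. In the present trial, all DLTs up to Amendment #4 were hematologic.

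A third tempting inference is that one missed AST event decides between expanding and closing. Closure is not automatic. Sections 11.1.1 and 11.2.2 leave room for expansion to 12 when two DLTs differ in class, and the example given there pairs hepatotoxicity with myelosuppression. The exception is conditional, however: one DLT must not appear dose-related, the effects must be readily reversible, and the named parties must agree. An unresolved elevation might not qualify.

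Finally, different ordering practice between sites is inferred from the missing requirement; the documents do not describe what sites order. The separate CRF packet and the redacted ABI-009 agent section cannot be checked. These replies reduce the expected frequency and consequence, but none supplies the missing requirement in Section 8.1.

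**Conclusion.** The inconsistency is confirmed by the text alone. AST and GGT are part of the DLT definition and its recovery exclusion, yet no baseline or on-study value of either is required. The gap covers only DLT-level AST or GGT elevations not mirrored in weekly ALT or bilirubin. Their rate is not given and is probably low at 15 mg/m², so no reliable size can be put on the effect; the figures above show only how the passing rule responds to assumed rates. It is a minor point, worth correcting because the remedy is cheap and the decision rests on few patients. The documents do not support the claims that liver toxicity is unmonitored, that a missed event must change the fate of the dose level, or that the adult event shows what to expect here.

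**What to change.** Add AST to the creatinine, ALT and bilirubin row of the Section 8.1 schedule, run on the same sample as ALT: pre-study, weekly in Cycles 1 and 2, and before later cycles. In the same edit settle GGT, either by scheduling it or by removing it from the DLT text. Adding AST alone would leave the same mismatch for GGT. Then align Sections 5.5.1.1, 8.1 and 11.2.1 and Appendix XV, so that the tests needed for DLT evaluability are the tests that the DLT rule uses. Stating that hepatic DLTs are judged on ALT and bilirubin alone would also make the text consistent, but it would narrow the DLT definition and should be an explicit decision by the sponsor.

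The cost is one or two extra analytes on a draw already taken, with no new visit or procedure. The downside is that a few more DLTs may be recorded.

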5.1.2 Cycle 2 and subsequent cycles

Temozolomide will be administered orally at 125 mg/m²/dose (maximum 250 mg/dose) once daily x 5 on Days 1-5 of each cycle. The dosing nomogram is included in [Appendix IV](#). If emesis occurs within 30 minutes of taking a dose of temozolomide, then the dose may be repeated once. If emesis occurs after 30 minutes, the dose should not be repeated. Instructions for administration of oral temozolomide to young children are included in [Appendix V](#).

Irinotecan will be administered orally at 90 mg/m²/dose once daily x 5 on Days 1-5 of each cycle. Irinotecan should be administered one hour after the administration of temozolomide. If emesis occurs within 30 minutes of taking a dose of irinotecan, then the dose may be repeated once. If emesis occurs after 30 minutes, the dose should not be repeated. Guidelines for the administration of oral irinotecan are included in [Appendix VI](#). Instructions for the preparation and administration of oral irinotecan are included in [Appendix VII](#).

If a dose of temozolomide or irinotecan is missed and less than 6 hours have passed since the scheduled dosing time, the dose should be taken immediately. If more than 6 hours have passed since the scheduled dosing time, the patient should not take the missed dose but should wait and take the next regularly scheduled dose.

Aprepitant is a substrate and moderate inhibitor of CYP3A4. Single aprepitant or fosaprepitant doses appear to only weakly inhibit CYP3A4 and are permitted. However, longer regimens (aprepitant administered on 2 or more consecutive days) may cause moderate CYP3A4 inhibition and should be avoided if reasonable alternatives exist.

Pre-Amendment #4: ABI-009 will be administered intravenously over 30 minutes on Day 1 and Day 8 of each cycle (beginning at Dose Level 1 = 35 mg/m²/dose; see dose escalation table in [Section 5.3.1](#)). ABI-009 should be given within 8 hours following administration of temozolomide and irinotecan. The use of in-line filters is NOT necessary. Upon completion of infusion, the infusion catheter should be flushed with normal saline.

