5.5 Definition of Dose-Limiting Toxicity (DLT)

DLT will be defined as any of the following events that are possibly, probably or definitely attributable to protocol therapy. The DLT observation period for the purposes of dose-escalation will be Cycles 1 and 2 of therapy.

Dose limiting hematological and non-hematological toxicities are defined differently.

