9.3.2 Toxicity

Incidence	Toxicities

Common (> 20% of patients)
	
 • Anemia • Thrombocytopenia • Neutrophil count decreased • White blood cell count decreased • Nausea • Vomiting • Constipation • Anorexia • Fever • Asthenia • Cholinergic symptoms: (rhinitis, increased salivation, miosis, lacrimation, diaphoresis, flushing, and intestinal hyperperistalsis that can cause abdominal cramping and diarrhea) • Alopecia • Bilirubin increased • Mucositis • Dyspnea • Cough • Weight loss • Pain

Occasional (4-20% of patients)
	
 • Abdominal fullness • Flatulence • Vasodilation • Hypotension • Dehydration • Edema • AST increased • Alkaline phosphatase increased • Ascites • Jaundice • Febrile neutropenia • Infection • Headache • Dizziness • Chills • Insomnia • Rash • Dyspepsia • Somnolence • Thromboembolic events • Pneumonia

Rare (≤ 3% of patients)
	
 • Anaphylaxis • Bradycardia • Disorientation/confusion • Colitis • Renal failure (secondary to severe dehydration)

	
 • Ileus • Pancreatitis • Pneumonitis (L)
Pregnancy & Lactation	Fetal toxicities and teratogenic effects of irinotecan have been noted in animals at doses similar or less than those used in humans. Toxicities include: decreased skeletal ossification, multiple anomalies, low birth weight and increased fetal mortality. It is not known if irinotecan is excreted into breast milk but it is excreted into rat milk.

(L) Toxicity may also occur later

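### Amylase and lipase are not required after any combination dose in children who stop during or after Cycle 2, so laboratory-only DLTs could go unrecorded in that half of the DLT window

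*Combined protocol and SAP*

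**What the plan says.** The Section 8.1 table has three timing columns: pre-study, Cycles 1 and 2, and prior to subsequent cycles. The row for "Amylase, Lipase" has a pre-study entry, a single draw before Cycle 2 in the middle column, and an entry in the last column. That last column is tied to a further cycle: "Studies may be obtained within 72 hours prior to the start of the subsequent cycle". Electrolytes, creatinine/ALT/bilirubin and lipids are weekly through both cycles. Tumour evaluation is due at the end of each of them.

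Four other provisions bear on this.

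- Section 5.5: "The DLT observation period for the purposes of dose-escalation will be Cycles 1 and 2 of therapy".
- Section 5.5.1.1 counts "Any Grade 3 or greater non-hematological toxicity attributable to the protocol therapy", apart from listed exclusions. The enzyme exclusion covers ALT, AST and GGT; amylase, lipase and pancreatitis are not listed.
- Sections 5.1.1 and 5.1.2: Cycle 1 is ABI-009 alone, and irinotecan and temozolomide start in Cycle 2.
- Section 8.1, footnote 12: a child with progression in Cycle 1 may still enter Cycle 2, but "Patients must have at least stable disease to continue to Cycles 3 and later".

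**The concern.** The protocol chose to monitor these enzymes, but the schedule does not span the window in which DLTs are counted. The draw before Cycle 2 precedes all irinotecan and temozolomide. The next is triggered only by starting Cycle 3, which depends on disease status, laboratory recovery and toxicity. Whether a DLT component is ascertained in the combination period therefore depends on the child's course.

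Under Section 11.3.1, dose level -2 is tolerable with at most 1 DLT in 6 evaluable children, and the study closes with 2 or more. Under Section 11.2.2, DLTs in the PK expansion cohort count as well. One unrecorded event could change the decision, and only in one direction.

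**Working it through.** The plan states no figure on this point, so the check sets the provisions side by side and then asks how large the effect could be.

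**Required amylase/lipase draws**

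| Period | Child who starts Cycle 3 | Child who stops during or after Cycle 2 |
|---|---|---|
| Pre-study | 1 | 1 |
| Before Cycle 2 (ABI-009 exposure only) | 1 | 1 |
| From Cycle 2 Day 1 to before Cycle 3 | 1 | 0 |

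Coverage is identical up to the start of Cycle 2; the whole difference lies in the combination half of the window. Weekly chemistry gives about three samples in the same 21 days.

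**Does another provision close the gap?** Section 10.1 keeps the Section 8.1 observations going for children removed in Cycle 1. After removal in a later cycle it asks only for what clinical care needs. Section 11.2.1 makes DLT evaluability depend on appropriate toxicity monitoring but does not say which tests that means. A child with every scheduled test done and no enzyme value after the combination can therefore be counted as evaluable without DLT.

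**Children without a required value.** The share not starting Cycle 3 is not given. At an assumed 30-60%, 6 × 0.30 = 1.8 and 6 × 0.60 = 3.6, so about 2 to 4 of 6. These are untested children, not missed DLTs.

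**Effect on the decision.** Let *p* be the rate of other DLTs, *q* the rate of laboratory-only enzyme DLTs in Cycle 2, and *f* the share not starting Cycle 3, treated as independent. None of the three is given in the documents.

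- Rate seen if every child is tested: 1 − (1 − *p*)(1 − *q*)
- Rate seen under the present schedule: 1 − (1 − *p*)(1 − *q*(1 − *f*))
- Chance of passing at DLT rate *r*: P(at most 1 of 6) = (1 − *r*)⁶ + 6*r*(1 − *r*)⁵

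The only related rate in the documents is irinotecan pancreatitis, listed as rare (at most 3%) in Section 9.3.2. It is a clinical event, so 3% is only a stand-in for *q*.

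| Assumed *q* | Assumed *p* | Assumed *f* | Rise in P(at most 1 of 6) |
|---|---|---|---|
| 1% | 10-30% | 30-60% | at most 0.012 |
| 3% | 10-30% | 30-60% | 0.013 to 0.035 |
| 5-15% | 10-25% | 25-75% | 0.02 to 0.24 |

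Worked example from the last row, with *p* = 20%, *q* = 10%, *f* = 50%. The rate with full testing is 1 − 0.80 × 0.90 = 0.28, which passes with probability 0.464. The rate seen is 1 − 0.80 × 0.95 = 0.24, which passes with probability 0.558.

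Expected missed events at *q* = 3%: 6 × 0.30 × 0.03 = 0.05 to 6 × 0.60 × 0.03 = 0.11 per six children.

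**The case against.** The strongest reply concerns consequence rather than the reading of the table.

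- *Not required is not the same as not measured.* The Cycle 2+ schema shows an evaluation on Day 21, and pre-cycle bloods may be drawn before the continuation decision is known. A reader might infer that no child who stops after Cycle 2 has a value. The documents show only that none is required.
- *Clinical pancreatitis is covered.* History and physical examination are weekly in Cycles 1 and 2, and Section 10.1 requires follow-up of events emerging within 30 days of the last dose of investigational agent. The entry "Pancreatitis" in the irinotecan table does not show that such cases would be missed.
- *There is little sign of a laboratory signal.* Amylase or lipase elevation is not in the irinotecan or temozolomide toxicity tables, among the adult ABI-009 toxicities in Section 2.3.1, or among the DLTs of the earlier temsirolimus combination study in Section 2.1.4. All DLTs seen before Amendment #4 were haematological. The ABI-009 agent section is redacted, so nothing can be inferred from it.
- *A DLT needs attribution* to protocol therapy, and the study chair's evaluability decisions are reviewed weekly (Section 14.4.2).
- *The schedule may be a deliberate lower-frequency tier*, since height/weight and performance status follow the same pattern.

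The first four points stand, and they limit the matter to attributable laboratory-only elevations of unknown and probably low frequency. The last is possible, but no reason is given for leaving the combination half of the window without a required value in some children. Weekly review does not help where no sample was requested.

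**Conclusion.** The scheduling gap is real. It is selective, because reaching Cycle 3 needs at least stable disease, and an event missed through it can only lower the DLT count. Its size is unknown and probably small: a few hundredths on the chance of passing the 1-of-6 rule if laboratory-only DLTs occur in about 3% or fewer. Rises of 0.1 or more appeared only with assumed rates of 10-15%, for which the documents give no basis.

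Two stronger readings should be resisted. One is that two to four of six children would have missed DLTs; that range counts untested children, under an assumed continuation rate. The other is that the dose level -2 decision is unreliable; the documents do not show that. Albumin follows the same schedule, but no argument links it to a DLT decision, so it is left out.

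This is a cheap improvement to DLT ascertainment, not a flaw that undermines the design.

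**What to change.** In the Section 8.1 table, change the Cycles 1 and 2 entry for amylase and lipase to: *End of Cycles 1 and 2, whether or not the next cycle is given*, run on the chemistry sample already scheduled. Align Section 10.1 so that the required Section 8.1 observations continue to the planned end of Cycle 2 for children removed during Cycle 2, matching what it already does for Cycle 1.

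The cost is two extra assays on an existing draw for children who stop after Cycle 2. For those removed during Cycle 2, it is continuing the scheduled observations to the planned end of that cycle. The gain has a limit: a Day 21 value falls 16 days after the last irinotecan dose (21 − 5) and 13 days after the Day 8 ABI-009 dose (21 − 8), so a transient elevation can still be missed.
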